Comparison of LigaSure to Conventional Electrocoagulation in Video-assisted

Thoracoscopic Surgery Lobectomy

NCT03125798

June 10,2016

Aim: to compare the short-term results of and extent of surgical injury by the LigaSure device and monopolar electrocautery in patients undergoing VATS lobectomy with lymphadenectomy.

Type of study: Pragmatic, parallel group, randomized controlled trial, simple randomization, 1:1 allocation ratio

Approval: Bioethics Committee of the Poznan University of Medical Sciences, Poznan, Poland

Location: Department of Thoracic Surgery, Poznan University of Medical Sciences

Inclusion criteria: admission for VATS lobectomy and lymphadenectomy for suspected or confirmed primary lung cancer, age of 18 years or older, ability to read and understand the information regarding the study, and ability to give informed consent to participate.

Exclusion criteria: preoperative radiotherapy or chemotherapy, prior mediastinoscopy or other surgical procedures involving the mediastinum, and ipsilateral chest surgery. Patients who underwent conversion from VATS to thoracotomy were assessed for the relationship between conversion and intervention, but their data were excluded from the final analysis to avoid confounding.

Enrollment: by the thoracic surgeons at admission to the department

Interventions: tissue dissection with the LigaSure device (the study group) or dissection with monopolar device (the control group).

Concealment: to conceal assignments, sequentially numbered, opaque, sealed envelopes that will be prepared before the study and will be opened just before the surgery. From this point, patients' assignments will be known to the surgeons.

Surgery: after induction of general anesthesia, a temperature probe will be inserted into the patient's esophagus and positioned at the level of subcarinal nodes. VATS lobectomy and lymphadenectomy will be performed with either the monopolar device or the LigaSure device. At the end of the surgery, one 24-F chest tube will be inserted into the pleural cavity and connected to a digital drainage system. The chest tube will be removed after resolution of air leak and when the fluid volume was <250 mL for 24 h.

The primary outcome measure: postoperative drainage volume

Secondary outcome measures: change in the esophageal temperature at the level of the subcarinal lymph nodes during lymphadenectomy and C-reactive protein levels 72 h after surgery.

Data collection:

1. Preoperative data: baseline characteristics, comorbidities, results of pulmonary function tests, laboratory tests results, and results of preoperative risk assessment.
2. Surgery data: approach, type of lobectomy, numbers of lymph nodes and lymph node stations removed, duration of surgery, and estimated blood loss, esophageal temperature

3. Postoperative data: ICU admission, 24-hour and 48-hour and total volume of chest tube drainage, chest tube duration, laboratory evaluation of the pleural fluid composition after 24-hours (WBC, triglycerides, albumin), hospital stay, complications

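### Dropping patients converted to thoracotomy after allocation does not avoid confounding and can bias the primary comparison

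*Protocol*

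**What the plan says.** The rule stands under Exclusion criteria in the protocol, although it concerns an event during the operation. Converted patients "were assessed for the relationship between conversion and intervention", "but their data were excluded from the final analysis to avoid confounding".

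The surrounding text fixes the order of events:

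- **Eligibility** is set at "admission for VATS lobectomy and lymphadenectomy for suspected or confirmed primary lung cancer" (Inclusion criteria).
- **Allocation**: the sealed envelopes "will be opened just before the surgery", and from then on "assignments will be known to the surgeons" (Concealment).
- **Design**: "Pragmatic, parallel group, randomized controlled trial" (Type of study).
- **Data**: the Data collection list includes "Surgery data: approach, type of lobectomy" and "24-hour and 48-hour and total volume of chest tube drainage".

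The SAP names no intention-to-treat or other analysis set and plans no analysis that keeps converted patients. It does not say whether conversions count towards its 10% dropout allowance.

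**The concern.** A true exclusion criterion acts before allocation and applies equally to both arms. This one acts afterwards. Conversion comes during an operation assigned to one of the two devices, carried out by a surgeon who knows the arm. The documents do not say who decides on conversion or by what criteria. That the operating surgeon decides is the natural reading, but it is an inference.

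The stated reason does not hold. Randomisation deals with baseline confounding in expectation, and selecting on a later event cannot improve on that. It can undo it: if conversion is related to drainage, and the arms differ in how many or which patients convert, the patients left are no longer comparable. If converted patients would drain more, the arm with more conversions looks better than it is; if less, worse. A positive or a null primary result could then partly reflect who was removed, and a reader could not tell.

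The final comparison is also of completed VATS procedures, whereas a trial described as pragmatic would be expected to compare the arms as randomised.

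**Working it through.** **Plan's own figure.** The SAP (sample size paragraph) gives SD 250 mL, a difference of 125 mL, two-sided 5%, 10% dropout and 107 per group for at least 85% power. A two-sample t calculation gives 95.4% at 107 per group and 93.1% at 96 (107 × 0.9). The claim is true as a lower bound. By the normal approximation the stated inputs need only 72 per group, or 80 with dropout, so 107 is not reproduced. That is a separate matter, and nothing below depends on it.

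**Size of the bias.** The documents give no conversion rate and no drainage figures for converted patients, so these inputs are assumptions. A share p of each arm is high-risk and drains s mL more. Only high-risk patients convert, a fraction c of them. The device has no effect. After exclusion, the mean excess left in an arm is

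s × p × (1 − c) / (1 − p × c),

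and the bias is the difference between arms. One arm has c = 20%; the other has 50% or 80%. Type I error uses SE = 250 × √(2/96) = 36.1 mL and a normal shift.

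| p | s (mL) | Conversion, arm 1 vs arm 2 | Bias (mL) | Type I error |
|---|---|---|---|---|
| 10% | 250 | 2% vs 5% | 7.3 | 5.5% |
| 10% | 250 | 2% vs 8% | 15.0 | 7.0% |
| 10% | 500 | 2% vs 5% | 14.5 | 6.9% |
| 10% | 500 | 2% vs 8% | 29.9 | 13.2% |
| 15% | 250 | 3% vs 7.5% | 10.7 | 6.0% |
| 15% | 250 | 3% vs 12% | 22.4 | 9.5% |
| 15% | 500 | 3% vs 7.5% | 21.3 | 9.1% |
| 15% | 500 | 3% vs 12% | 44.8 | 23.7% |

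Worked example, last row: 500 × 0.15 × 0.8 / 0.97 = 61.9; 500 × 0.15 × 0.2 / 0.88 = 17.0; difference 44.8 mL. If the high-risk group is also allowed to widen the SD, with 107 per group less conversions, the last row falls to 20.0% and the range is 5.5% to 20.0%. These figures assume a t or normal test; the SAP moves to Mann-Whitney when normality or equal variance fails.

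**Other cases.**
- s = 0, or the same c in both arms: bias 0.
- Equal 5% conversion, but only high-risk patients in one arm and random patients in the other: s × p − s × (p − 0.05)/0.95 = 11.2 to 23.7 mL. Equal rates alone do not protect.
- A simpler model, bias = (difference in conversion rates) × D, where D is the converters' excess drainage: 10% vs 5% with D = 125 gives 6.25 mL, and 15% vs 5% with D = 500 gives 50 mL (type I error 28.4%).

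**Planned check of conversion by arm.** Power at 107 per arm, by exact enumeration:

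| Conversion rates | Fisher | SAP's rule (chi-square if all expected counts exceed 5) |
|---|---|---|
| 2% vs 5% | 11% | 13% |
| 5% vs 10% | 21% | 29% |
| 3% vs 12% | 65% | 74% |

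**Power if converted patients are kept.** Assume that a fraction k converts in each arm, that converted patients show no device effect and that they drain s mL more. The effect is then 125 × (1 − k) and SD = √(250² + k(1 − k)s²). Noncentral t is used, approximate because the mixture is not normal. Each cell gives power at 107 / 96 per group.

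| k | s = 0 | s = 250 | s = 500 | Exclusion analysis, starting from 107 |
|---|---|---|---|---|
| 5% | 93.3 / 90.6% | 92.2 / 89.2% | 88.7 / 85.1% | 94.5% |
| 10% | 90.6 / 87.3% | 88.1 / 84.4% | 80.2 / 75.8% | 93.1% |
| 15% | 87.2 / 83.4% | 83.0 / 78.8% | 71.2 / 66.4% | 91.8% |

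**The case against.** **The target may be completed VATS.** The aim concerns patients undergoing VATS lobectomy, and the planning data come from VATS patients. Including thoracotomies mixes the trauma of the incision into drainage and CRP, and the stated reason may be loose wording for that worry. This is a legitimate interest, but simple exclusion after allocation does not give comparable groups for it.

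**The check on conversion by arm.** It could reveal a large imbalance: 74% power for 3% vs 12% under the SAP's rule. It is weak for moderate differences, no action follows from its result, and it cannot see arms that convert different kinds of patients at similar rates.

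**The bias may be small.** This stands as a point about size. Every input is assumed, seven of the eight scenarios give at most 30 mL, and six keep type I error below 10%. Confidence attaches to the principle, not to a demonstrated effect on this trial.

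**Keeping converted patients costs power.** This stands too. At 96 per group, five of the nine scenarios fall below the SAP's 85%. But a power loss can be calculated and planned for, whereas selection bias of unknown size and direction cannot, and a larger sample does not remove it.

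**Conclusion.** The concern holds. The rule is explicit, it acts after allocation, the reason given for it is incorrect, and nothing in the SAP restores the patients. It governs the primary comparison, so it should be changed before the result is relied on.

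The claim is that exclusion can bias the result, not that it has done so. There is no bias if conversion is unrelated to drainage within each arm, or if the same kinds of patients convert at the same rates in both. The documents show neither. The illustrations range from zero to about 45 mL in the high-risk-group model, and to 50 mL in the simpler one, against a 125 mL target. For the 45 mL case, type I error is 20-24%, depending on how the SD is treated.

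**What to change.** Delete the exclusion from the protocol and add a short population paragraph to the SAP:

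- **Primary analysis:** all randomised patients who have surgery, in their allocated arm, converted or not (modified intention-to-treat), on total drainage.
- **Sensitivity analysis:** completed VATS only, labelled as such.
- **Conversions:** numbers and reasons, by arm.
- **Oesophageal temperature:** the reading during lymphadenectomy whatever the approach. Where none could be taken after conversion, treat it as missing and report the number missing by arm.

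**Cost.** The text change is one protocol sentence and one SAP paragraph, with no extra patients or procedures. Two assumptions need confirming: that total drainage and 72-hour CRP are obtainable for converted patients (the data list does not mention them separately), and that the approach field records conversion. The rule is written in the past tense, so data set aside may have to be recovered and reanalysed.

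Against the exclusion analysis from 107 per group, the power loss is about 1-2, 3-5 and 5-9 points at 5%, 10% and 15% conversion with a shift up to 250 mL. With a 500 mL shift it is about 6, 13 and 21 points. The SAP should say whether its 85% still holds. Under the fix that needs 98 evaluable per group at 10% conversion with a 250 mL shift, 114 at 15% with 250 mL, and 152 at 15% with 500 mL. The planning SD comes from VATS patients and may not cover thoracotomy.

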Comparison of LigaSure to Conventional Electrocoagulation in Video-assisted Thoracoscopic Surgery Lobectomy, NCT03125798 June 10, 2016

This study was powered for superiority in accordance with the data for total chest drainage volume in patients after VATS lobectomy and lymphadenectomy with monopolar electrocautery; these data were obtained from the institutional database (2013–2015; $n = 278$). If the mean total postoperative chest drainage volume were 750 ± 250 mL, and if the dropout rate were 10%, a sample of 214 patients (107 patients per group) would provide at least 85% power to detect a clinically important difference of 125 mL for this endpoint between the two groups, according to two-sided tests with a 5% level of significance.

The analyzed data were calculated as means \pm standard deviations, medians, minimum and maximum values, interquartile ranges (IQRs; quartile 1 to quartile 3), or percentages, as appropriate. We used the Shapiro–Wilk test to check normality of distribution and Levene’s test to check equality of variances. To compare the two unpaired groups, we used the unpaired t test for data that followed a normal distribution and had homogeneity of variances; otherwise, we used the Mann–Whitney U test. To analyze categorical data, we used the χ^2 test when the sample size was larger than 40 and all expected values were greater than 5; for other situations, we used Fisher’s exact test or the χ^2 test with Yates’s correction; or the Fisher-Freeman-Halton test for contingency table larger than 2×2 with any expected values was less or equal to 5. All results were considered significant when $p < 0.05$. To perform statistical analyses, we used Statistica 13.0 (StatSoft, Dell, Round Rock, TX, USA) or StatXact 11.0 (Cytel, Cambridge, MA, USA).

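### Envelopes are opened before the chest is explored, so some randomised patients may have no VATS lobectomy with lymphadenectomy, and the plan has no rule for them

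*Protocol*

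**What the plan says.** The Protocol's Aim limits the question to results "in patients undergoing VATS lobectomy with lymphadenectomy". Its Inclusion criteria require "admission for VATS lobectomy and lymphadenectomy for suspected or confirmed primary lung cancer", and Enrollment is done "by the thoracic surgeons at admission to the department". Under Concealment, assignments are held in "sequentially numbered, opaque, sealed envelopes that will be prepared before the study and will be opened just before the surgery", and then: "From this point, patients' assignments will be known to the surgeons".

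The Surgery paragraph describes one operation for everyone: "VATS lobectomy and lymphadenectomy will be performed with either the monopolar device or the LigaSure device". The only rule for a randomised patient whose operation does not go as planned is under Exclusion criteria. It covers conversion to thoracotomy: those patients are assessed for a link with the intervention, "but their data were excluded from the final analysis to avoid confounding".

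The SAP takes its drainage figures (750 mL, SD 250) from institutional patients who had already had the full operation with monopolar cautery. It allows for loss with the phrase "if the dropout rate were 10" percent, but does not say what that loss consists of. It defines no analysis population.

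**The concern.** Allocation becomes known before the chest is explored. A lesion that is only suspected to be cancer may prove benign, and disease may prove unresectable. A patient in whom that happens has been randomised but has little or none of the dissection being compared, and may have no esophageal temperature change during lymphadenectomy, which is a secondary outcome.

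The plan leaves two ways to treat such a patient and chooses neither:

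- **Kept in.** The patient contributes a drainage volume that the device hardly influenced. This shrinks the difference between arms and may widen the spread.
- **Taken out.** The exclusion follows an operative decision made with the arm known, so the two analysed groups are no longer protected by randomisation.

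Either way, the analysed population is settled after allocation rather than by the design.

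**Working it through.** **The plan's own figure.** SAP inputs: difference 125 mL, SD 250 mL, two-sided 5%, 107 per group, 10% dropout. Evaluable per group: 107 × 0.9 ≈ 96. Two-sample t-test power (noncentral t) is 95.4% at 107 per group and 93.1% at 96. For 85% power, 73 per group suffice, or 73 / 0.9 ≈ 81 to 82 after dropout. The claim of at least 85% is therefore true, with room to spare.

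**Patients without lobectomy, kept in.** The documents give neither their share *q* nor their drainage. Assumptions: *q* from 3% to 10%, mean 300 mL, SD 150 mL, no device effect in them. For an arm whose lobectomy patients have mean *m* (750 or 625 mL):

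- difference between arms = 125 × (1 − *q*)
- arm variance = (1 − *q*) × 250² + *q* × 150² + *q*(1 − *q*) × (*m* − 300)²

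Example at *q* = 8%:

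- Difference: 125 × 0.92 = 115 mL.
- Variance, *m* = 750: 57,500 + 1,800 + 0.0736 × 450² = 74,204.
- Variance, *m* = 625: 57,500 + 1,800 + 0.0736 × 325² = 67,074.
- Average variance 70,639, so the pooled SD is about 266 mL. Power at 96 per group is 84.7%.

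| Share without lobectomy | Difference (mL) | Pooled SD (mL) | Power, 96 per group | Power, 107 per group |
|---|---|---|---|---|
| 0% | 125 | 250 | 93.1% | 95.4% |
| 3% | 121 | 256 | 90.3% | 93.1% |
| 5% | 119 | 260 | 88.2% | 91.3% |
| 8% | 115 | 266 | 84.7% | 88.3% |
| 10% | 112.5 | 269 | 82.2% | 86.1% |

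If these patients instead drain like control lobectomy patients (750 mL, SD 250), power at 10% and 96 per group is 87.0%.

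**Patients without lobectomy, removed.** If they fall within the 10% dropout, power stays at the planned 93.1%. If 10% are lost on top of it, 107 × 0.9 × 0.9 ≈ 87 per group remain and power is about 90.5%.

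**Unequal shares.** If these patients stay in and their share differs by 5 points between arms, the mean difference shifts by 0.05 × (750 − 300) = 22.5 mL. That is 22.5 / 125 = 18% of the difference the trial is sized to detect. Both the imbalance and the 450 mL gap are assumptions.

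**The case against.** The strongest reply has four parts.

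1. **The event is not documented.** Eligibility requires admission for this very operation, and the Protocol says that it will be performed; "suspected" describes the diagnosis, not the procedure. This stands in part. A reader might infer that patients without lobectomy are in fact randomised and dilute the comparison. The documents show only that it can happen and that nothing provides for it.

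2. **Power is not threatened.** This largely stands. A reader might infer that the trial is underpowered, but the sample is larger than 85% power needs. Power falls below 85% only if about 8% or more are kept, they drain far less, and a full 10% dropout occurs as well.

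3. **No bias mechanism is shown.** Benign or unresectable findings have no obvious link to the choice of device. This stands against any claim that exclusions would be biased. It does not remove the point that they would rest on decisions taken with the arm known and with no written rule.

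4. **The timing is already good, and an analysis-set sentence would do.** Late opening of sealed, opaque, numbered envelopes protects concealment and limits loss after allocation compared with opening at admission, so a reader should not infer that concealment is defective. A written analysis set would help, but alone it still has to keep unexposed patients or exclude them on an unblinded decision. It is also true that the intervention is defined as tissue dissection generally, so a later opening takes any earlier adhesiolysis or biopsy out of the comparison. That is a real cost.

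**Conclusion.** The point holds as a gap in the design and an opportunity for a cheap improvement. It does not show bias or a shortfall in power. Allocation is revealed before it is certain that the patient will have the operation named in the aim; the surgeon then knows the arm; and neither document says how a patient without that operation is handled or analysed.

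The cost in power is modest: from 93.1% to between 90.3% and 82.2% for an assumed 3% to 10% of patients kept at 300 mL (SD 150), with 96 per group. Those inputs are all assumptions, because the documents give none. The stronger reason to act is that the randomised population would match the aim, with no need for exclusions decided with the arm known. The handling of conversions to thoracotomy is a separate issue and is not judged here.

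**What to change.** Change the Concealment paragraph along these lines: *The envelope is opened in the operating room after thoracoscopic exploration, once the surgeon has recorded that VATS lobectomy with lymphadenectomy will proceed, and before lobectomy or nodal dissection starts. Consented patients who do not reach this point are logged as not randomised.*

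Add to the SAP: *Any randomised patient who nevertheless has no lobectomy is reported by arm and kept in the allocated arm.* The SAP should also say whether the 10% dropout is meant to include such patients.

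The cost is a few sentences, with the same envelopes and staff. Both devices must be available in the room, and any adhesiolysis or biopsy before the envelope is opened is no longer part of the device comparison.

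### The esophageal temperature change is compared without adjustment, which can give away some precision; a reading taken before the device is used should be the covariate

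*Protocol*

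**What the plan says.** The protocol lists as a secondary outcome the "change in the esophageal temperature at the level of the subcarinal lymph nodes during lymphadenectomy". Under Surgery it says that "after induction of general anesthesia, a temperature probe will be inserted into the patient's esophagus and positioned at the level of subcarinal nodes", and then that "VATS lobectomy and lymphadenectomy will be performed with either the monopolar device or the LigaSure device". So the probe is in place early, and the allocated device is used for both parts of the operation. Under Concealment, the assignment envelopes "will be opened just before the surgery". Under Data collection, temperature appears only as a named item among the surgery data, with no time points. Nothing says which two readings form the change, or whether lymphadenectomy comes before or after the lobectomy dissection.

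The SAP has one rule for all continuous outcomes: "To compare the two unpaired groups, we used the unpaired t test for data that followed a normal distribution and had homogeneity of variances". When either condition fails, the plan moves to the rank-based Mann–Whitney test, which is also unadjusted. It names no regression model, covariate or confidence interval for any outcome.

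**The concern.** A change score subtracts the start value with its coefficient fixed at 1. If the true within-arm slope of the later temperature on the start temperature is not 1, the subtraction corrects too much or too little. The leftover start-temperature variation then adds noise to the arm comparison. Allocation is by simple randomization, so nothing in the design limits a chance difference in start temperature between the arms. A linear model estimates the slope instead of fixing it.

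The obvious covariate is the start reading itself, but it may not be clean. If lymphadenectomy follows the lobectomy dissection, a reading at its start already comes after use of the allocated device. It could then be affected by the treatment, and adjusting for it would change what is estimated as well as its precision.

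The stake is modest but real. The protocol's aim includes the extent of surgical injury, and this is the only temperature measure among its outcomes. The plan reports no interval for it and leaves its two readings undefined.

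**Working it through.** **Plan's own figure.** There is none for this outcome. The SAP's sample size of 214 (107 per group) concerns drainage volume only. It is used here just for scale: 107 less 10% dropout leaves about 96 per arm.

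**Assumed inputs.** r is the within-arm correlation of start and later temperature, and k is the later SD divided by the start SD. The documents give neither, so a range is shown.

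**Step 1: gain when the covariate is the start reading, taken before device use.** In units of the start variance:
- variance of the change: 1 + k² − 2rk
- residual variance after adjustment: k²(1 − r²)
- ratio, adjusted to unadjusted: k²(1 − r²) / (1 + k² − 2rk), which becomes (1 + r)/2 when k = 1

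| k | r = 0.5 | r = 0.7 | r = 0.9 |
|---|---|---|---|
| 1 | 0.75 | 0.85 | 0.95 |
| 1.5 | 0.96 | 1.00 | 0.78 |
| 2 | 1.00 | 0.93 | 0.54 |

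The slope is rk. The gain vanishes when rk = 1, for example at k = 2, r = 0.5, or at k = 1.25, r = 0.8.

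**Step 2: what this means for power.** Take a true difference at which the unadjusted t test has 80% power, so the standardized difference is 1.960 + 0.842 = 2.802. With adjustment, power is Φ(2.802/√ratio − 1.960). For k = 1:
- r = 0.5: 2.802/√0.75 = 3.235, power 89.9%
- r = 0.7: 2.802/√0.85 = 3.039, power 86.0%
- r = 0.9: 2.802/√0.95 = 2.874, power 82.0%

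**Step 3: gain when the covariate is a separate, earlier reading.** If c is the within-arm correlation between that reading and the change, the ratio is 1 − c². A 25% cut needs |c| = 0.5; a 5% cut needs |c| = √0.05 = 0.22. The documents do not give c. When the earlier reading is also the start reading, c = (rk − 1)/√(1 + k² − 2rk). At k = 1, r = 0.5 this is −0.5, which returns the 0.75 above.

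**Step 4: why a post-device start reading is a poor main covariate.** Let T be the device effect on the later temperature and h the part already present at the start reading. Let b be the within-arm slope. With assumed T = 0.5 and h = 0.2:
- change during lymphadenectomy: T − h = 0.30
- later temperature adjusted for the post-device start: T − bh = 0.40, 0.36 or 0.32 for b = 0.5, 0.7 or 0.9
- later temperature adjusted for a pre-device reading: T = 0.50

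The first is the effect during lymphadenectomy and the last is the effect of the whole operation. The middle figures are neither, and they move with b. A model of the change on arm and a pre-device reading still estimates 0.30, the quantity that the protocol names.

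**The case against.** The strongest case against is that nothing in the planned analysis is invalid. If the start reading precedes device use, the unadjusted comparison of changes is unbiased under randomization, and a chance imbalance costs precision, not validity. This stands.

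Second, the size of the gain is assumed. If the later reading is the start reading plus an independent rise, the slope is 1 and the gain is zero however large the rise. Two readings from the same probe could well be close to that. This also stands. The 46% cut at k = 2, r = 0.9 is the edge of a chosen grid and not an expectation.

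Third, a reader might infer that adjustment can never lose. That holds only in large samples and only against the t test. The SAP moves to Mann–Whitney when normality or equal variance fails, and there the direction depends on the distribution. In simulations with 96 per arm and assumed values, a lognormal rise (log-SD 0.8, 40% larger in one arm) gave Mann–Whitney 82% power and the linear model 70%. An exponential rise (50% larger) gave 67% and 79%. This is why the planned test should be kept alongside the model.

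Fourth, a reader might infer that the plan understates the device effect because heat from the lobectomy is subtracted. The documents do not support this. The order of the two steps is not stated, and the protocol confines the outcome to lymphadenectomy, so earlier heat is outside its definition. The possibility bears on the choice of covariate; it does not show bias.

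**Conclusion.** The point holds as a minor efficiency and definition issue on a secondary outcome. The plan needs a start temperature for every patient, has a probe in place from induction, and uses neither in the comparison. With a start reading taken before device use, equal SDs and r from 0.5 to 0.9, adjustment would cut the variance by 25% to 5%. That is equivalent to moving from 80% power to between 90% and 82%. At a slope of 1 it would bring nothing. With a separate pre-device reading the cut is c², which is unknown. All of these figures rest on assumed correlations and SD ratios.

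It does not follow that the planned test is invalid, that the trial will understate the device difference, or that a linear model is certain to beat the rank test. What the documents do show is that the readings forming the change are undefined. They also leave open that a start-of-lymphadenectomy reading comes after device use, which rules it out as the main covariate unless the order is settled.

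**What to change.** 1. In the protocol, state which two readings form the change, and log one reading after the probe is placed and before the allocated device is first activated.
2. In the SAP, make the main analysis of this outcome a linear model of the temperature change on arm and that pre-device reading. When the pre-device reading is also the start reading, this is ordinary ANCOVA.
3. Report the adjusted between-arm difference with a 95% CI from robust standard errors, which allow for unequal variances.
4. Keep the planned t test or Mann–Whitney test as a sensitivity analysis.
5. If heat from the whole operation is of interest, add as a supplementary estimate the temperature during lymphadenectomy adjusted for the pre-device reading, with the reading used for it defined in advance.

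The cost is a few sentences and one extra logged value from a probe already in place, with no added patients or procedures. The downside is that the gain in precision may turn out small.

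### CRP at 72 h is compared as an unadjusted level; using preoperative CRP as a covariate would recover precision at small cost

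*Protocol*

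**What the plan says.** The Protocol (Secondary outcome measures) names two outcomes. Temperature is defined as a "change in the esophageal temperature at the level of the subcarinal lymph nodes during lymphadenectomy". CRP is defined as a single value, "C-reactive protein levels 72 h after surgery", with no reference to a value before surgery.

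Under Data collection, item 1 (preoperative data) includes "laboratory tests results, and results of preoperative risk assessment" but does not say which tests, so CRP is neither named nor ruled out. Item 3 (postoperative data) has one laboratory entry, on pleural fluid: "laboratory evaluation of the pleural fluid composition after 24-hours (WBC, triglycerides, albumin), hospital stay, complications". It names no postoperative blood test.

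The SAP's analysis paragraph gives one method for continuous data in two unpaired groups: the t test if normality and equal variances hold, otherwise the Mann-Whitney U test. It has no covariate adjustment and no rule for missing values. Type of study in the Protocol specifies simple randomisation, 1:1.

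**The concern.** CRP is the only blood marker among the named outcomes that bears on the trial's aim of comparing the extent of surgical injury. Patients with suspected or confirmed lung cancer and varying comorbidities may differ in CRP before any device is used. If that variation persists to 72 h, an unadjusted comparison carries it in full. It widens the confidence interval for the device effect, and because simple randomisation does nothing to balance baseline CRP, one arm may by chance start higher. Both can be reduced by using a preoperative value, which the plan may already be collecting.

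A smaller issue is whether the 72-h value will exist for everyone. The outcome is named, but it is missing from the postoperative data list, and the plan does not say what happens if a patient has left before 72 h.

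**Working it through.** **The plan's own figure.** The documents give no sample size, SD or expected difference for CRP. The only calculation is for drainage: "mean total postoperative chest drainage volume were 750 ± 250 mL", with "at least 85% power to detect a clinically important difference of 125 mL", 107 per group and 10% dropout. The usual formula gives 2 × (1.960 + 1.036)² × (250/125)² = 71.8, so 72 per arm, and 72/0.9 = 80 with dropout. The stated 107 is larger. After 10% dropout it leaves 107 × 0.9 ≈ 96 per arm and about 93% power, so the power statement is true although 107 is not reproduced. That is a separate matter. The 96 per arm is used below.

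**Inputs for CRP.** n = 96 per arm (from the SAP). r = correlation between preoperative and 72-h CRP on the scale of analysis: not in the documents, assumed 0.3 to 0.5. Results are in units of the within-arm SD of 72-h CRP.

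**Precision.** Unadjusted standard error of the difference = √(2/n) = √(2/96) = 0.144 SD. With baseline as covariate, the residual variance is multiplied by 1 − r²; the loss of one degree of freedom is negligible here.

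| Assumed r | Variance removed, r² | Standard error, 0.144 × √(1 − r²) | Interval shorter by | Unadjusted patients per arm for the same precision, 96/(1 − r²) |
|---|---|---|---|---|
| 0 | 0% | 0.144 | 0% | 96 |
| 0.3 | 9% | 0.138 | 5% | 105 |
| 0.5 | 25% | 0.125 | 13% | 128 |

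**Chance imbalance.** The arm difference in mean baseline CRP has mean zero and standard error √(2/96) = 0.144 baseline SD, so 95% of randomisations fall within ±1.96 × 0.144 = ±0.283. An imbalance at that edge moves the unadjusted 72-h difference by r × 0.283: 0.08 SD at r = 0.3 and 0.14 SD at r = 0.5. The direction is random, and the average over randomisations is zero. This is the same variance as in the table, seen from the baseline side, and not an additional cost.

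**Would a change score do instead?** Temperature is defined as a change, so the same might be considered for CRP. If the SDs before surgery and at 72 h were equal (an assumption), the variance of the change is 2(1 − r) times that of the level: 1.4 at r = 0.3 and 1.0 at r = 0.5. A change score would then be worse than the raw level or no better, whereas ANCOVA gives 0.91 and 0.75. The remedy is therefore a covariate and not a redefinition as change.

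**Availability of the 72-h value.** Secondary outcome measures requires it and Data collection item 3 does not list it. Neither document has a discharge criterion, a minimum stay, or a provision for sampling after discharge. Hospital stay is recorded, but no planning figure for it is given.

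**The case against.** The strongest reply is that the unadjusted comparison is valid. Randomisation balances preoperative CRP in expectation, so the planned test is unbiased, and adjusting a secondary outcome is an improvement and not the correction of an error. That stands. A reader might infer that inflammation present before surgery would be counted as device injury; in a randomised between-arm comparison it would not, except through chance imbalance. It is also fair that CRP may already be among the preoperative tests, and that r is unknown. With r near zero the gain disappears.

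A reader might infer from item 3 that the 72-h CRP would not be drawn. That goes too far: this is a single-department trial and the outcome is named directly above the list. The omission is missing detail.

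The most tempting stronger reading is that the SAP's figures show unequal loss of CRP samples. The Protocol's tube rule is "The chest tube will be removed after resolution of air leak and when the fluid volume was <250 mL for 24 h". A total below 500 mL means that one of the first two 24-h periods was below 250 mL, so the fluid part is met by 48 h. With a normal distribution, SD 250 mL and means of 750 and 625 mL, the shares below 500 mL are P(Z < −1) = 15.9% and P(Z < −0.5) = 30.9%. The arithmetic is right, but the inference is not supported:

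- The SAP gives no stay or discharge figure and no direction for the 125 mL.
- Tube removal also requires resolution of air leak, and it is not discharge.
- The 500 mL total is not the rule itself: a patient draining 500 mL and then 200 mL also meets the fluid part at 48 h. Cut-offs from 250 to 750 mL give gaps of 4.4 to 19.1 percentage points.
- Dropping everyone below 500 mL would shrink the drainage difference from 0.50 to 0.28 SD, but that figure applies to CRP only if the whole CRP effect runs through drainage. If instead there is no CRP effect and CRP correlates 0.1 to 0.5 with drainage within arm (assumed), the shift is about 0.02 to 0.11 SD, even with all of these patients lost.
- If no patient leaves before 72 h, there is no effect at all.

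**Conclusion.** The point holds as one of efficiency. The 72-h CRP is compared as a raw level without a baseline covariate, so preoperative variation remains as noise and possible chance imbalance. Adjustment would remove about 9% to 25% of the residual variance, on the assumption that r is 0.3 to 0.5 and the relation is roughly linear on the scale analysed. The planned comparison is not biased by the omission.

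The unsecured 72-h sample is a lesser point. Unequal loss between arms is a conditional risk of unknown size. It needs a real drainage effect, air leak not governing tube removal, and tube removal leading to discharge before 72 h, and the documents establish none of these. It should not be presented as a consequence of the SAP's figures. It justifies recording and reporting missing values, and no more.

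**What to change.** 1. In Data collection item 1, name serum CRP among the preoperative laboratory tests.
2. In the SAP, specify that 72-h CRP is compared between arms by ANCOVA with preoperative CRP as covariate, on the log scale if skewed (effect then reported as a ratio of geometric means). State this before outcome data are seen.
3. In Data collection item 3, list the 72-h CRP, and in the SAP state that the number of patients without a 72-h value will be reported by arm.

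The cost is one preoperative assay per patient if CRP is not already measured, a few lines of text, and a slightly longer analysis. The sample size and the primary outcome are unaffected. A preoperative value that was never measured cannot be recovered at analysis, so item 1 has to be settled before enrolment.
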